7.2.5. Observation period

The duration of observation will be 60 weeks (14 months) from the date of treatment commencement (Day 1). However, patients who are treated with XELJANZ for more than 60 weeks after the date of treatment commencement will be continuously followed up until the end of the investigation period * (June 2021). For patients who discontinue XELJANZ, information until the discontinuation will be collected.

*: Date of the last observation before June 2021

This study will be conducted using booklet type CRF. Investigator will complete each booklet of CRFs for each observation period in Table 1. However, for patients who discontinue XELJANZ, information until the discontinuation will be collected.

Name of CRF	Observation period
Booklet 1	Treatment commencement to Week 26 (Month 6) of treatment
Booklet 2	Week 27 (Month 7) to Week 60 (Month 14) of treatment
Booklet 3	Week 61 (Month 15) to end of the investigation period (June 2021)

Table 1. Name of CRF and observation period

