7.3.9. Status of pregnancy (female patients only)

The status of pregnancy from the date of commencement of XELJANZ treatment to the date of completion of the observation period (or date of XELJANZ discontinuation) should be recorded. However, for patients who are treated with XELJANZ for more than 60 weeks after the date of treatment commencement, the status of pregnancy until the end of the investigation period (or date of XELJANZ discontinuation) should also be recorded.

7.3.10.Status of treatment with XELJANZ

The status of treatment with XELJANZ at the completion of the observation period for each booklet (Week 26, Week 60, end of the investigation) should be confirmed, and the following information should be recorded. If the reason for discontinuation at the last observation is an adverse event or patient's death, its details should be recorded in the adverse event field.

- 1. Date of the last observation
- 2. Completion of treatment or reason for discontinuation
 - Completed (treatment continued)
 - Adverse events (Record the details in the adverse event field)
 - Patient's death (Record the date of death)
 - Remission
 - Insufficient clinical effectiveness
 - Failure to show up
 - Other

7.3.11.Adverse events

The status of occurrence of adverse events from the date of commencement of XELJANZ treatment to the date of completion of the observation period (or date of XELJANZ discontinuation) should be confirmed, and the following information should be recorded. However, for patients who are treated with XELJANZ for more than 60 weeks after the date of treatment commencement, the record of malignant tumor and adverse events leading to discontinuation that occur at and after Week 61 should include the following information.

Occurrence of a serious adverse reaction, an unexpected adverse reaction or other adverse reactions should be separately investigated in detail if determined necessary by Sponsor.

- Presence/absence of adverse event
- Name of adverse event
- Diagnosis of malignant tumor (only if malignant tumor occurs)
- Date of occurrence
- Intervention
- Seriousness
- Outcome at the completion of observation period
- Causal relationship

If the adverse event is associated with abnormal laboratory values, i.e., clinical laboratory tests, the following information should also be recorded.

- Laboratory parameter
- Site reference value
- Unit
- Date measured

• Results

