With regard to analyses that involve the time to onset of each element in the safety specification, if development of an event has been reported in a patient but its onset date is unknown, the onset date will be imputed with the last date on which the patient can be confirmed to be free from the event in view of all kinds of data collected; the shortest possible date imputed may be the start date of treatment. For patients in whom development has not been reported but the date of the end of observation is unknown, the end date will be imputed with the last date on which administration of this drug can be confirmed in view of all kinds of data collected; the shortest possible date imputed may be the start date of treatment.

Missing data (including the case of "unknown") for candidate covariates (Section 6.4) will not be imputed in univariate analyses. For multivariate analyses, missing data for candidate covariates will be treated as a subcategory of the category "unknown".

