- Malignancy
- Cardiovascular events (including lipids increased and hyperlipidaemia)
- Cardiovascular events (excluding lipids increased and hyperlipidaemia)
- Lipids increased and hyperlipidaemia
- Rhabdomyolysis and myopathy

In addition, patients who experienced adverse reactions in the scope of the safety specification will be summarized in terms of n and proportion by SOC and PT, for different kinds of action taken and outcome.

Timing of onset of elements in the safety specification

Patients who experienced adverse reactions of each element in the safety specification will be summarized by timing of first onset, in terms of n and proportion as well as incidence and its 95% CI. For the purpose of summarization by time to onset, the denominator to calculate the proportion will be the number of patients who took at least one dose during each time category, and the denominator to calculate the incidence will be the duration of exposure in each time category. The categories for onset timing will be given by $[\le 15 \text{ weeks}, > 15 \text{ to} \le 30 \text{ weeks}, > 30 \text{ to} \le 45 \text{ weeks}, > 45 \text{ to} \le 60 \text{ weeks}]$, except for malignancy, for which given by ≤ 15 weeks, ≥ 15 to ≤ 30 weeks, ≥ 30 to ≤ 45 weeks, ≥ 45 to ≤ 60 weeks, ≥ 60 to ≤ 75 weeks, >75 to ≤ 90 weeks, >90 to ≤ 105 weeks, >105 to ≤ 120 weeks, >120 to ≤ 135 weeks, >135 weeks].

Relationship between concomitant drugs and adverse reactions

To investigate the relationship between concomitant biologics/immunosuppressants or concomitant CYP3A4 inhibitors/CYP2C19 inhibitors and adverse reactions included in the scope of the safety specification, development of those adverse reactions will be summarized in patients with and without concomitant use of a biologic/immunosuppressant and in patients with and without concomitant use of a CYP3A4 inhibitor/CYP2C19 inhibitor, by PT in terms of number of patients. Concomitant drugs used after the first onset of a target event will be excluded from the summarization. Concomitant drugs considered in this investigation include:

- Biologics (including recombinants)/immunosuppressants: abatacept, adalimumab, anakinra, azathioprine, baminercept, canakinumab, certolizumab, certolizumab pegol, cyclosporine, efalizumab, etanercept, golimumab, infliximab, ofatumumab, rituximab, Syk kinase inhibitors, tacrolimus hydrate, tocilizumab, sarilumab, zanolimumab, vedolizumab, ustekinumab, secukinumab, ixekizumab, and 6-mercaptopurine

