8.2.3.3. Subgroup analyses

Analyses by dosage subgroup

(1) Safety analysis of the treatment with 10 mg BID

To evaluate the safety of the treatment with this drug administered mainly at a dose of 10 mg BID, the following analyses will be performed in the patients treated mainly at 10 mg BID defined in Section 5.4.1 and results will be compared with those in the entire SAS. To eliminate the effect of including patients who discontinued treatment during the induction phase, similar analyses will also be performed in patients treated mainly at 10 mg BID for a long term and results will be compared with those in the patients treated for a long term defined in Section 5.4.1:

- Adverse reactions of each element in the safety specification will be summarized in terms of number and proportion of patients as well as incidence and its 95% CI.
- Adverse reactions will be summarized by SOC and PT in terms of number and proportion of patients.

In addition, to investigate the temporal change in the risk of occurrence of each event, the following analyses will be performed in the patients treated mainly at 10 mg BID and results will be compared with those in the SAS:

- Patients who experienced adverse reactions of each element in the safety specification will be summarized by timing of first onset, in terms of n and proportion as well as incidence and its 95% CI. For the purpose of summarization by time to onset, the denominator to calculate the proportion will be the number of patients who took at least one dose during each time category, and the denominator to calculate the incidence will be the duration of exposure in each time category. The categories for onset timing will be given by [\leq 15 weeks, >15 to \leq 30 weeks, >30 to \leq 45 weeks, >45 to \leq 60 weeks], except for malignancy, for which given by [\leq 15 weeks, >15 to \leq 30 weeks, >30 to \leq 45 weeks, >45 to \leq 60 weeks, >60 to \leq 75 weeks, >75 to \leq 90 weeks, >90 to \leq 105 weeks, >105 to \leq 120 weeks, >120 to \leq 135 weeks, >135 weeks].
- A Kaplan-Meier plot will be presented for the time to first onset of each element in the safety specification.
- (2) Evaluation of dose response of the safety

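### Unknown onset dates are always imputed to the earliest compatible day, so a constant risk can look front-loaded in the onset bands and Kaplan-Meier plots, and no sensitivity analysis is planned

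*SAP*

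**What the plan says.** SAP section 7 covers analyses that involve time to onset of a safety-specification element. If an event was reported but "its onset date is unknown", then "the onset date will be imputed with the last date on which the patient can be confirmed to be free from the event". That date is to be found "in view of all kinds of data collected", and "the shortest possible date imputed may be the start date of treatment". The section does not define what confirms a patient as event-free. It makes no provision for a recorded month or year, and plans neither a count of imputed dates nor a sensitivity analysis.

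The onset date is used in three places:
- the onset-timing tables in SAP 8.2.3.1 to 8.2.3.3 (15-week bands to Week 60, longer for malignancy; band incidence uses the exposure inside the band);
- the Kaplan-Meier plots (SAP 8.1.5 and 8.2.3.3);
- the concomitant-drug summaries, where "Concomitant drugs used after the first onset of a target event will be excluded from the summarization".

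For patients treated mainly at 10 mg BID, SAP 8.2.3.3 gives the purpose of the bands and plots: "to investigate the temporal change in the risk of occurrence of each event". It states a similar purpose for the comparison of higher and lower dose levels.

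Protocol 7.3.11 lists "Date of occurrence" among the items recorded for each adverse event. In Protocol 7.2.5, Booklet 1 covers "Treatment commencement to Week 26 (Month 6) of treatment", Booklet 2 covers Weeks 27 to 60, and Booklet 3 covers the time after that.

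**The concern.** The true onset lies somewhere between the last day the patient was known to be free of the event and the first day it was known to be present. The rule always takes the lower end and never uses the upper end. Its error therefore has one direction, and it falls on the question the bands and plots are meant to answer. An apparent early peak followed by a decline could come from the data or from the rule, and the planned output would not let a reader tell which.

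Malignancy has no 60-week cap, so its dates can move furthest. For a patient who started in May 2018, Booklet 3 runs for about 100 weeks. If only booklets serve as anchors, an undated malignancy from Booklet 3 moves back to about Week 60.

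Unknown dates need not be blank fields. SAP section 7 also treats inconsistent data as missing.

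**Working it through.** **Inputs.** The plan gives no figure for this rule, so there is none to reproduce. From the documents: 470 patients, an assumed true herpes zoster rate of 8 per 100 person-years (Protocol 7.5), 60 weeks of observation and 15-week bands. Assumed here: a constant hazard, treatment stopping at 0.45 per year (60% still treated at Week 60), and a share *m* of events with unknown onset, from 5% to 20%.

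**Step 1: true picture.** Event and stopping hazards sum to 0.53 per year, and 15 weeks is 0.2875 years (52.18 weeks per year). Person-years in band 1 are 470/0.53 × (1 − e^(−0.53×0.2875)) = 886.8 × 0.1413 = 125.3. Each later band is 0.8587 times the one before: 107.6, 92.4, 79.3. At 8 per 100 the expected events are 10.0, 8.6, 7.4 and 6.4, about 32.4 in 405 person-years. Let E = 18.63 events fall in the first 30 weeks and L = 13.74 in the last 30.

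**Step 2: Day 1 for every unknown date (the floor).** Band 1 receives (1−m) of its own events plus m of all events. At m = 0.20 that is 0.8×10.02 + 0.2×32.37 = 14.49, or 14.49/125.3 = 11.6 per 100. The later bands fall to 0.8 × 8 = 6.4.

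**Step 3: booklet anchors only.** An event before Week 26 goes to Day 1, and a later one to Week 26. Events before Week 26 are 886.8 × 0.08 × (1 − e^(−0.53×26/52.18)) = 16.46, which leaves 15.91.
- Band 1: (0.8×10.02 + 0.2×16.46)/125.3 = 9.0
- Band 2: (0.8×8.61 + 0.2×15.91)/107.6 = 9.4
- Bands 3 and 4: 6.4

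**Step 4: early-to-late ratio.** In steps 2 and 3 every undated late event moves into the first 30 weeks. With person-time unchanged, the ratio is (1 + m×L/E)/(1 − m), where L/E = 0.737:
- m = 5%: 1.037/0.95 = 1.09
- m = 10%: 1.074/0.90 = 1.19
- m = 20%: 1.147/0.80 = 1.43

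**Step 5: simulation at m = 20%.** Exposure here also ends at the imputed onset. The visit anchors are SAP Appendix 1 weeks 2, 4, 8, 12, 16, 24, 32, 40 and 48.

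| Event-free anchor | Bands 1/2/3/4 per 100 PY | First 30 / last 30 weeks |
|---|---|---|
| True | 8.0/8.0/8.0/8.0 | 1.0 |
| Visit weeks | 8.1/8.1/8.1/7.7 | about 1.03 |
| Booklets only | 9.1/9.4/6.5/6.4 | about 1.43–1.44 |
| Day 1 for all | 11.7/6.5/6.5/6.4 | about 1.44 |

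Overall incidence stays at about 8.0 to 8.1 in every row.

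**Step 6: precision.** With the SAP 8.1.4 interval, 10 events in 125 person-years give limits of (100/125)×4.80 = 3.8 and (100/125)×18.39 = 14.7 per 100.

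**Step 7: alternatives, booklet anchors, m = 20%.**
- *Separate row for undated events:* each band reads 0.8 × 8 = 6.4, which is flat but 20% low.
- *Latest compatible date:* only undated events from Weeks 26 to 30 leave the early half, at most 0.2 × (18.63 − 16.46) = 0.43. The ratio is [(18.63 − 0.43)/232.9] / [(13.74 + 0.43)/171.7] = 7.81/8.25 = 0.95.
- *Midpoint date:* 9.1/6.4/9.8/6.4. This is near balance overall, but bands 1 and 3 are inflated.

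**The case against.** The strongest reply is that the start of treatment is only a floor. The rule looks for the last event-free day "in view of all kinds of data collected", and the CRF offers later anchors: dated laboratory tests, effectiveness ratings, presence or absence of adverse events, and the booklet split. A reader might infer that undated events pile into the first band, with band 1 at about 1.8 times the later bands (11.7/6.4). The documents do not support that as the expected result. It needs every unknown date to fall to Day 1, against the rule's own wording. With booklet anchors the larger rate is in band 2, and with visit anchors the distortion nearly vanishes.

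That reply does not settle the matter. The SAP does not say that a visit week proves a patient event-free. The Appendix 1 windows apply to Mayo scores and faecal calprotectin, and the data are extracted from charts. The result can therefore range from the visit-week row to the Day 1 row according to a programming choice.

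Other parts of the reply stand:
- The unknown share is not documented. Onset date is a CRF field, the sponsor queries CRFs, and laboratory events carry a measurement date, so the share may be small.
- With about 10 events in a band, the interval of roughly 4 to 15 per 100 would hide modest shifts.
- The timing tables are descriptive, and overall counts and incidence hardly move.
- The SAP does not say that the person-time in 8.1.4 or the concomitant-drug counts use imputed dates. A reader might infer that cases are systematically misclassified as not exposed to a drug. That is possible when a drug was started between the imputed and the true onset, but it is inferred and unquantified. A drug in use on Day 1 would not be lost.
- Nothing in the documents shows that absence of malignancy is rarely recorded.

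**Conclusion.** The point holds as a one-directional bias of unknown size in the timing analyses. It is worth correcting, but it does not threaten the primary safety results. With 20% unknown dates and a constant 8 per 100 person-years, the early-to-late ratio is about 1.03 with visit anchors and about 1.43 to 1.44 with booklet-only or Day 1 anchors. At 5% and 10% unknown, the unfavourable anchors give 1.09 and 1.19. These figures rest on an assumed missing share, a constant hazard and an assumed stopping rate. They show what the rule could do, not what it will do in this study.

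The documents do not support reading the rule as placing undated events on Day 1 in general, or as distorting overall incidence. They do show a rule whose anchor is undefined, whose error runs only backward, and for which no sensitivity analysis is planned.

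**What to change.** Amend SAP section 7 and the onset-timing text in 8.2.3.1 to 8.2.3.3 as follows.

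1. In the onset-timing tables, show events with an imputed onset in a separate 'onset unknown' row, with the number imputed for each element. Keep them in the overall n, proportion and incidence.
2. State which records confirm a patient as event-free, and use any recorded month or year and the CRF booklet to narrow the interval.
3. Keep the earliest-date rule for the main Kaplan-Meier plots. Repeat the plots and the band tables with the latest compatible date as a sensitivity analysis. In the booklet-only example the two runs give early-to-late ratios of about 1.43 and 0.95, which bracket the true 1.0.
4. In the concomitant-drug summaries, do not drop a drug solely because of an imputed onset.

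A midpoint date is not proposed as the main rule. Under booklet anchors it creates artificial peaks of its own.

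The cost is SAP wording, one extra table row and one repeat run. Band rates will be lower in proportion to the undated events (6.4 instead of 8.0 at 20% unknown). A footnote should say so and state how the exposure of those patients is counted.

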8. STATISTICAL METHODS AND ANALYSES

8.1. Statistical Methods

8.1.1. Continuous variables

For continuous variables, summary statistics (n, mean, standard deviation [SD], median, maximum, minimum) will be presented.

8.1.2. Categorical variables

For categorical variables, patients (or another kind of relevant elements) included in each category will be summarized in terms of n and proportion.

8.1.3. Binary variables

For binary variables, patients included in each binary category will be summarized in terms of n and proportion. The two-sided 95% confidence interval (CI) will be determined using an exact method if a CI should be determined for the proportion.

When comparisons of the proportion should be made between subgroups, their risk ratios (RRs) will be presented with corresponding 95% CIs. Each RR and its 95% CI will also be presented graphically (See Appendix 2).

8.1.4. Analyses based on the person-year method

The incidence of an event per exposure duration will, if it should be presented, be calculated using the following formula:

Incidence (patients/100 patient-year) = $100 \times y/PT$

y: Number of patients who experienced the event

PT: Total exposure duration (years),

Here the exposure duration for event-free patients will be given by the period from the start of treatment to the end of the observation period unless this exceeds 60 weeks; if this period exceeds 60 weeks, the exposure duration should be 60 weeks. The exposure duration for patients who experienced the event is, in principle, the period from the start of treatment to the day the event was first observed, but if the event occurred 60 weeks or later after the start of treatment, the patient will be handled as an event-free patient and their exposure duration should be 60 weeks. For malignancy, however, no such upper limit will be set; the exposure duration for malignancy-free patients will be the period from the start of treatment to the end of the observation period, while the exposure duration for patients in whom malignancy developed will be the period from the start of treatment to the day of the first observation of the event. The 95% CI will be calculated using the following formula:

$$\left[\frac{100}{PT} \times \frac{1}{2} \chi_{2y}^{2}(\alpha/2), \frac{100}{PT} \times \frac{1}{2} \chi_{2(y+1)}^{2}(1-\alpha/2)\right]$$

y: Number of observed events

 $\chi^2_{2\nu}(\alpha/2)$: The $\alpha/2$ -fractile point of the chi-square distribution with 2y degrees of freedom

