8.1.5. Analyses of time-to-event data

Kaplan-Meier plots will be presented for time-to-event data. Event-free patients will be censored at the end of their observation period or 60 weeks after the start of treatment, whichever came first. If the time to event exceeds 60 weeks, the patient will be treated as event-free and censored at 60 weeks. For malignancy, however, no such upper limit will be set for the time to onset, and malignancy-free patients will be censored at the end of their observation period.

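### SAP 8.1.4 defines y as patients in the incidence rate but as events in its confidence interval, and treats an event at exactly 60 weeks differently from 8.1.5

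*SAP*

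**What the plan says.** SAP 8.1.4 gives the incidence as 100 × y / PT, in patients per 100 patient-years, with "y: Number of patients who experienced the event". For a patient with the event, exposure is in principle "the period from the start of treatment to the day the event was first observed". For an event-free patient it runs to the end of observation, and "if this period exceeds 60 weeks, the exposure duration should be 60 weeks". Malignancy has no 60-week cap.

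The section continues: "The 95% CI will be calculated using the following formula". The limits are the usual chi-square form of the exact Poisson interval, with the same symbols y and PT. The legend beneath them reads "y: Number of observed events". It does not say whether this means first events or all occurrences.

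On the 60-week limit, 8.1.4 says that "if the event occurred 60 weeks or later after the start of treatment, the patient will be handled as an event-free patient". SAP 8.1.5 says: "If the time to event exceeds 60 weeks, the patient will be treated as event-free and censored at 60 weeks". The last onset band in SAP 8.2.3.1, 8.2.3.2 and 8.2.3.3 for elements other than malignancy runs from above 45 weeks up to and including 60 weeks.

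**The concern.** A rate and its interval should be built on the same count. PT stops at the first event, so a second event in the same patient has no person-time behind it. Adding it to the interval's y raises both limits while the rate stays where it was.

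More than one event per patient within an element is foreseeable. SAP 8.2.3.1 has rules for patients with repeated reactions of the same preferred term. SAP 6.1 also pools many terms into single elements: one combines neutrophil, lymphocyte and haemoglobin decreases, and another lists dozens of lipid terms. A patient can therefore contribute several events to an element without any single event recurring.

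Incidence with its 95% CI is planned for each safety-specification element, for adverse reactions and for adverse events. It also appears in the onset-timing tables and, for adverse reactions, in the dose subgroups, so an ambiguous input to the formula reaches many tables.

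The 60-week clash is a separate matter. An event exactly on the boundary falls inside the last onset band and is an event in the Kaplan-Meier analysis, but 8.1.4 removes it from the incidence. The count and the incidence in one table row could then rest on different numerators.

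**Working it through.** **Inputs from the documents.** Both definitions of y, PT ending at the first event, and the interval formula come from SAP 8.1.4. The 8 and 4 per 100 person-years, the 470 and the 495 come from Protocol 7.5 and SAP 2.1.

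**Inputs assumed.** The documents give no event counts, no total exposure and no number of events per patient. I take PT = 400 patient-years and 20 patients with the event, and vary the event count from 20 to 30.

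**The plan's own figures.** Registration reproduces: 470 / 0.95 = 494.7, so 495. The 470 cannot be reproduced from the stated inputs, because mean exposure per patient is not given. With a single Poisson count in the exact interval, the 80% probability is first reached at 282 patient-years (19 or more events needed, probability 80.1%). That is 282 / 470 = 0.60 patient-years per patient, an inferred value. The double definition of y does not enter that calculation.

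**Formula.** Lower limit = (100/PT) × ½ × χ²(0.025; 2y). Upper limit = (100/PT) × ½ × χ²(0.975; 2(y+1)). With PT = 400, each chi-square value is multiplied by 100/400 × ½ = 0.125.

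**Rate.** 100 × 20 / 400 = 5.0 per 100 patient-years in every row below.

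| y entered in the interval | χ² lower, upper | 95% CI | Contains 5.0? |
|---|---|---|---|
| 20 (patients) | 24.43, 61.78 | 3.05 to 7.72 | yes |
| 22 events | 27.57, 66.62 | 3.45 to 8.33 | yes |
| 25 events | 32.36, 73.81 | 4.04 to 9.23 | yes |
| 30 events | 40.48, 85.65 | 5.06 to 10.71 | no |

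**When the interval misses its own estimate.** This needs ½ × χ²(0.025; 2E) to exceed the number of patients n, where E is the number of events. PT cancels.

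| Patients n | Smallest E | E / n |
|---|---|---|
| 10 | 18 | 1.80 |
| 20 | 30 | 1.50 |
| 30 | 42 | 1.40 |
| 40 | 54 | 1.35 |

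**At the planning rate.** With 24 patients in an assumed 300 patient-years, the rate is 8.00 with CI 5.13 to 11.90. Entering 26 events gives 5.66 to 12.70, which is shifted but still contains 8.00. Exclusion needs 35 events (8.13 to 16.23).

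**With one definition.** If y is the number of patients in both places, the interval contained its estimate for every y checked, from 0 to 1999.

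**An event at exactly 60 weeks, side by side.**

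| Place | Treatment |
|---|---|
| SAP 8.1.4 (incidence) | event-free, exposure 60 weeks |
| SAP 8.1.5 (Kaplan-Meier) | event, since the time does not exceed 60 weeks |
| SAP 8.2.3.1 to 8.2.3.3 (onset bands) | inside the last band |

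SAP 6.1 and 8.2.3 take events up to the earlier of end of observation and 60 weeks. They do not address the boundary day explicitly.

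**The case against.** The strongest reply is that 8.1.4 already points to first events. It uses one symbol and one PT for both formulas, cuts exposure at the first event and expresses the rate in patients. The safety tables report patients, the timing tables use first onset, and Protocol 7.7.2.1 also puts patients in the numerator. No analysis in the plan counts recurrences. On that reading events equal patients, and the formula is the ordinary exact Poisson interval. The SAP is also an English translation from Japanese, so a single phrase may not carry the original's precision.

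Most of this stands: first events are the more coherent reading, and the chi-square formula itself is right. But the plan does not say so, and the legend as printed says something else. An analysis plan should not leave the input to its interval to inference.

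Two stronger conclusions are tempting. A reader might infer that every incidence interval is wrong or need not contain its estimate. The documents do not support this: it requires the all-occurrences reading, does not touch elements with at most one event per patient, and requires the large excesses tabulated above. A reader might also infer from the 25-event row, where the lower limit passes 4 per 100 person-years, that a study conclusion could change. That row rests on an assumed 1.25 events per patient at a rate of 5.0, below the planning rate of 8. In addition, SAP 4.2 states that no decision rules apply, so nothing is triggered at 4.

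**Conclusion.** The point holds as a low-severity inconsistency of definition. Under a literal reading of the interval's legend, the limits move upwards from the first extra event, and only in elements where patients have more than one event. Under the first-event reading nothing is wrong. The sizes shown rest on assumed counts and exposure, because the documents give no events-per-patient figure.

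The 60-week clash is real whichever way y is read, but it concerns only first events falling exactly on the boundary, which will be very few. Malignancy is exempt because its exposure is not capped. The sample size of 470 is unaffected by either point; the unstated exposure behind it is a separate question.

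**What to change.** In SAP 8.1.4, define y once, as the number of patients with at least one event (the first event), and state that this y is used in both the rate and the interval. Delete the second legend. In the same section, make the event-free rule apply to events later than 60 weeks, so that it matches 8.1.5 and the onset bands.

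The cost is two phrases in the SAP and a check that the incidence program enters the patient count in both formulas and handles the boundary day as the onset tables do. The wording should be compared with the Japanese original at the same time. No data collection or sample size changes.
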